**Table 1. Phase III Assessment Instruments.**

Measures/ Proposed Indicators	Purpose	Assessment Time Point			Description/Rationale
		BL	8 & 16 mo	24 mo	
Telephone Screen	E				Administered prior to the baseline assessment to determine initial eligibility. Assesses inclusion/exclusion criteria.
Contact Information	Contact	✓	✓	✓	Collected to verify Veteran status in CPRS, scheduling, send appointment confirmation letter, contact for follow-up, etc.
Demographic Questionnaire & Military History Form (DHMQ)	Demographic, PV	✓		✓	Assesses basic demographic and Veterans-specific characteristics (e.g., years of education, years of military service, family history of military service). Re-administered at annual to assess changeable demographics (e.g. marital status, employment).
Mini International Neuropsychiatric Interview (MINI)	E	✓			Modules administered from this widely used screening Interview to assess for exclusionary criteria (manic/hypomanic episode and psychosis).
Full Combat Experiences Scale (FCES)	PV	✓		✓	Self-report measure of exposure to combat situations (Hoge et al., 2004). Re-administered if re-deployed. Items added from the National Vietnam Veterans Readjustment Survey to assess potentially morally injurious combat events.
Nash Moral Injury Events Scale (MIES)	PV	✓		✓	Self-report questionnaire developed as a measure of exposure to potentially morally injurious events (Nash, et al, 2013). Re-administered if re-deployed. The MIES has excellent internal consistency, both the overall scale and the 2 subscales showed temporal stability, and early research found preliminary support for the construct validity (Nash, et al., 2013).
Deployment Risk and Resilience Inventory (DRRI)	PV	✓		✓	The DRRI (King, King, and Vogt, 2003) is a collection of scales assessing pre-deployment, deployment, and post-deployment risk and resilience factors. The DRRI was validated for use with OIF Veterans (Vogt et al., 2008). Scales administered will include the military sexual trauma scale at baseline and the post-deployment social support scale at baseline and 24 months.
Acquired Capability for Suicide Scale	PV	✓		✓	Self-report of perceived ability to tolerate fear and pain associated with suicide. Has adequate internal consistency in a study that built on SERVE (.80).
Interpersonal Needs Questionnaire (INQ)	PV	✓		✓	Self-report measure that assess thwarted belongingness and perceived burdensomeness (Van Orden et al., 2012). The INQ has demonstrated good convergent validity, internal consistency and concurrent validity (Van Orden et al., 2012).
Treatment Involvement Form (TIF)	CV	✓	✓	✓	Form created for the current study that will be used to assess treatment involvement during the prior interval, including medical, psychiatric and psychological treatment, as well as supportive interventions (e.g.

					Alcoholics Anonymous, Narcotics Anonymous).
Columbia Suicide Scale	DV	✓		✓	The Columbia Suicide Scale (Posner et al., 2008) is a state-of-the-art suicide assessment for individuals perceived to be at high risk for suicidality. Internal consistency ranged from .73 to .95 (Posner et al., 2011).
Clinician Administered NSSI Disorder Index (CANDI)	DV	✓		✓	The CANDI is a clinical interview that diagnoses Nonsuicidal Self Injury (NSSI) disorder and type and frequency of NSSI. Demonstrated good reliability and validity in prior research, including in Co-I [name]'s VA-funded study of NSSI in veterans. Administered in tandem with the NSSI Screen developed by Co-I [name].
Beck Scale for Suicide Ideation (BSSI)	DV, Med	✓		✓	Widely-used self-report measure of intensity of thoughts and behaviors associated with suicide. Includes 2 additional items that ask about past suicide attempts as well as the level of suicidal intent during the most recent attempt. Prior research shows that endorsement of suicidal thoughts and behaviors can be greater on self-report questionnaires compared to interviews. Thus, this measure complements the suicide focused interviews.
Suicide Cognitions Scale-Brief	DV, Med	✓		✓	Self-report measure of suicide-related thoughts that load onto the following subscales: unsolvability, unlovability, and unbearability. Brief version was recently validated across 3 chronic pain samples (Bryan et al., 2016).
PTSD Checklist-5 (PCL-5)	Med	✓	✓	✓	Self-report of symptoms of PTSD during the previous month. Demonstrates high sensitivity and specificity in relation to a lengthy diagnostic interview for PTSD (CAPS), with which it was co-developed. Strong psychometric properties, including in numerous Project SERVE papers.
Patient Health Questionnaire-9	Med, DV	✓	✓	✓	Self-report measure used for screening, diagnosing, and monitoring depression. It incorporates DSM-IV diagnostic criteria (Question 9 screens for suicidal ideation; Kroenke, Spitzer & Williams, 2001).
Alcohol Use Disorders Identification Test (AUDIT)	Med	✓	✓	✓	Self-report measure to screen for alcohol-use disorders (Saunders, Aasland, Babor, Fuente, & Grant, 1993). 10-item measures adopted by VA as the gold-standard screening for alcohol use disorders in mental health and primary care clinics. Good internal consistency ( $\alpha=.80$ - .94) and test-retest reliability ( $r=.86$ ), and strong concurrent validity with the MAST and CAGE screening measures (Babor et al., 2001).
Drug Abuse Screening Test (DAST)	Med	✓	✓	✓	Self-report measure to quantify drug misuse and related psychosocial impairment. Good internal consistency and concurrent validity with frequency of drug use over 12-months (Skinner, 1982). Moderately correlated with denial and social desirability. The instructions will be updated to more explicitly assess for misuse of opiates that may have been prescribed.
Substance Use Screen	Med	✓		✓	Form created for the current study that will be used to assess current and lifetime substance use (e.g., stimulants, cannabis, etc.)
TBI—Vasterling Assessment Interview	E, Med	✓		✓	This clinician-administered structured interview developed by Vasterling (2008) assesses the number, recency, type of injury, and clinical sequelae associated with traumatic brain injury during deployment. Total number of lifetime head injuries leading to any symptoms will also be assessed. TBI will be assessed at baseline for lifetime history and then re-assessed at the annual interview for any new TBIs that may have occurred during the past two years.
Ten-item Personality Inventory (TIPI)	PV	✓			10-item self-report measure of the Five-Factor Model of personality (Gosling, Rentfrow & Swann, 2003).
Patient Health Questionnaire-15 (PHQ-15)	Med, DV	✓		✓	Self-report (Kroenke, Spitzer & Williams, 2002) of somatic symptom clusters including pain (musculoskeletal, headaches), cardiac, gastrointestinal, respiratory, etc. that account for more than 90% of outpatient physical complaints (Kroenke, Arrington & Mangelsdorff, 1990). The PHQ-15 had strong internal reliability in the initial validation ( $\alpha=.80$ ) and was associated with functional status and disability (Kroenke et al., 2002).
Chronic Pain Screen Quest.	Med	✓		✓	Self-report of pain type/intensity. Internal consistency in SERVE was .67.

Acceptance and Action Questionnaire (AAQ-II)	PV	✓	✓	✓	Self-report measure assessing acceptance, experiential avoidance (attempting to alter the form or frequency of unwanted internal experiences), and taking action despite experiencing unwanted private events (Bond, et al., 2011). Strong psychometrics in multiple SERVE publications ([name] et al., 2013; 2018; in press, [name], [name], et al., 2017).
Brief Experiential Avoidance Quest. (BEAQ)	PV	✓	✓	✓	The BEAQ is a single-factor item that assesses the modifiable construct of experiential avoidance (Gamez et al., 2013).
Self-Compassion Scale – Short Form (SCS-SF)	PV	✓	✓	✓	Self-report measure of self-compassion, consisting of a total scale score and six subscale scores: self-kindness, self-judgment, common humanity, isolation, mindfulness, and over-identified (Neff, 2003; Raes, Pommier, Neff, & Van Gucht, 2011). The SCS-SF is strongly correlated with the original long form ( $r=.97$ ) and has the same 6-factor structure with one higher-order factor. Internal consistency was .86 for the whole measure, with subscale alphas ranging from .54 to .75 (Raes et al., 2011).
Difficulties in Emotion Regulation Scale (DERS-Brief)	PV	✓	✓	✓	Self-report measure (Bjureber et al., 2016) of 6 domains of emotion dysregulation: nonacceptance of emotional responses, difficulty engaging in goal-directed behavior, difficulty with impulse control, lack of emotional awareness, poor emotion coping strategies, and lack of emotional clarity.
Five Facet Mindfulness Questionnaire	PV	✓	✓	✓	Self-report measure assessing multiple facets of the modifiable factor of mindfulness. The FFMQ has demonstrated good construct validity and internal consistency. Good predictive validity in research with veterans.
World Health Organization Disability Assessment Schedule II (WHODAS 2.0)	DV	✓	✓	✓	Self-report assessment of functional disability with total score and 6 domains of functioning: understanding and communicating, mobility, getting along with others, life activities (i.e., work, education, household responsibilities), participation in society, and self-care (Üstün et al., 2010). Both global and specific areas of functioning are crucial in thoroughly understanding functional recovery, as Veterans may function well in one area and have difficulty in another. Moreover, some domains may be affected by contextual factors instead of representing functional capacity (e.g., work functioning in a struggling economy independent of impairment).
Inventory of Psychosocial Functioning (IPF) – Brief	DV	✓	✓	✓	Self-report measure (Co-I [name] et al., 2009; Bovin et al., 2018) of Romantic Relationships with a Spouse/Partner, Family, Work, Friendships and Socializing, Parenting, Education, and Self-Care. The short version has a .90 correlation with the full 80-item instrument (Co-I [name], personal communication). Higher scores indicate greater functional impairment.
Quality of Life Scale (QLS)	DV	✓	✓	✓	Self-report (Burkhardt, et al., 1989) assessing how satisfied people are in areas distinct from health status (mate, physical well-being, relationships with others, social, community, and civic activities, personal development and fulfillment, recreation, and independence). Good internal consistency and high test-retest reliability (Burkhardt et al. 2003).
Values Tracker	DV	✓	✓	✓	Brief self-report measure of value engagement. Good predictive validity in research with chronic pain samples.
Meaning in Life Questionnaire	PV	✓		✓	Brief self-report assesses presence and search for meaning in life (Steger et al., 2006).
Social Connection Index	DV, Med	✓		✓	Self-report measure of frequency of contact with others, number of close friends and relatives, level of secure attachment in relationships, frequency of problems getting along with friends and family members.
Brief Loneliness Measure	DV, Med	✓		✓	Brief self-report measure of loneliness for use in large survey studies. Highly correlated with lengthier measures such as the UCLA Loneliness Scale.
Interpersonal Reactivity Index-Brief (B-IRI)	DV, Med	✓			Brief self-report measure of disposition to empathic responding; 2 subscales assess perspective taking and empathic concern. Good reliability and validity (Ingooglia et al., 2016).
Flexible Regulation of Emotional	DV, Med	✓			Self-report measure of ability to enhance and suppress both positive and negative emotions. Good convergent and divergent validity with depression, personality, resilience, and laboratory tasks measuring

Expression (FREE) Scale				emotion suppression and enhancement (Burton & Bonanno, 2016).	
Perceived Ability to Cope with Trauma (PACT) Scale	DV, Med	✓		Self-report measure of trauma-focused and future-oriented coping. In addition, a coping flexibility score indicates greater use of both types of coping.	
Differential Emotions Scale-IV (DES-IV)	DV, Med	✓		Self-report of frequency of emotional responses across 9 types of emotions: guilt, shame, fear, anger, shyness, self-hostility, contempt, disgust, sadness. Good reliability and associations with personality and MH symptoms (Izard et al., 1993). Modified to assess participants' emotional responses to thinking about their most traumatic and potentially morally distressing experiences.	
Traumatic Life Events Questionnaire (TLEQ-Lite)	PV	✓	✓	24 items (Kubany et al., 2000); assesses frequency of exposure to 22 potentially traumatic events encountered outside of military service, resulting in a continuous trauma exposure score. The psychometric properties were carefully established in 5 studies, including a sample of combat Veterans (Kubany et al., 2000). Modified for this study to no longer assess DSM-IV criteria for PTSD Criterion A2, as this is no longer required in DSM-5, and to include an item assessing exposure to COVID-19 as a potential stressor.	
Multidimensional Psychological Flexibility Inventory (MPFI)	PV	✓	✓	60-item self-report (Rolffs, Rogge, & Wilson, 2018) used to assess the dimensions of the psychological flexibility model that underlies Acceptance and Commitment Therapy	
Expressions of Moral Injury Scale (EMIS)	DV			17-item self-report (Currier et al., 2018) to assess for problems associated with exposure to morally injurious events	
Credibility & Expectancy Questionnaire	PV			Widely-used 6-item self-report measure of the credibility of the treatment approach and expectations for positive response to the treatment (Borkovec & Nau, 1972). Used in [name] prior ACT studies (Hermann, [name] et al., 2016; [name] et al., in press).	
Client Satisfaction Questionnaire	DV			Widely-used 8-item self-report measure of treatment satisfaction (Larsen et al., 1979). Used in [name] prior ACT studies (Hermann, [name] et al., 2016; [name] et al., in press).	
Working Alliance Inventory	PV			Widely-used, brief self-report measure of clients' perceptions of working alliance with therapist on 3 dimensions: goal, task, and bond (Horvath, 1981).	
Parenting Stress Index Short Form (PSI-SF)	PV	✓	✓	✓	Veterans with a child between birth and 12 will be asked to complete this measure on the child they are most concerned about. Thirty-six items are divided into three domains: Parental Distress (PD), Parent-Child Dysfunctional Interaction (P-CDI), and Difficult Child (DC), which combine to form a Total Stress scale.
Quality of Marriage Index (QMI)	PV	✓	✓	✓	6-item self-report questionnaire used to measure relationship distress (Norton, 1983). The measure was developed based on an empirical analysis of the functioning and construction of marriage quality variables.
Saliva sample and saliva collection questionnaire	PV, Med	✓			DNA and other products will be extracted from saliva samples. A list of 13 questions will be asked during sample collection related to variables that can affect quality of saliva sample and associated biomarkers (e.g., time since last meal). Provision of saliva sample is optional.
Blood sample	PV, Med	✓			DNA and other products will be extracted from blood samples. Provision of blood sample is optional.

BL = Baseline; E = Eligibility; DV = Dependent/Outcome Variable; PV = Predictor Variable; Med = Mediator; CV = Covariate

**Training of Clinical Interviewers.** Clinical interviews will be conducted by trained interviewers familiar with the assessment procedures and the culture of military service. The PI and trained doctoral staff members will conduct certifications in the proper administration of the clinical interviews and will provide ongoing, weekly supervision of interviews conducted. Further, all interviews will be video or audio-recorded through a VA computer using a microphone directly onto the secure, approved drive behind the VA firewall or using a FIPS 140-2 validated digital voice recorder. In any instance in which technical or logistical difficulties interfere with video recording, audio recording will be used. All video/audio files will be stored on the secure, approved drive

behind the VA firewall. FIPS 140-2 validated digital voice recorders will only be transported by research staff who have an approved Authorization to Transport memorandum on file with the Research Office. After being uploaded to these secure folders, audio files will be accessible to approved research staff. Approved research staff will listen to recordings for training purposes (e.g., practice coding, learn administration procedures), or for the purposes of assessing inter-rater reliability. An interviewer training manual has been developed, which details the training method, scoring procedures, and process for systematic DRG to ensure consistency across interviewers ([name], [name] & [name], unpublished). Interviews (10% or more if necessary) will be rated for inter-rater reliability as an added measure. Recordings will also be coded for observable, clinically relevant behaviors.

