**Assessment Procedures.** The assessment instruments for Phase III are presented in Table 1 (see attached). Assessment domains were selected based on the empirical literature to capture biopsychosocial variables associated with responses to stressful life events and include: 1) pre-deployment characteristics (demographic variables, pre-deployment psychiatric history; pre-deployment stress and trauma); 2) cognitive functioning; 3) deployment related stress, trauma, exposure to potentially morally injurious events, and TBI (number of deployments, deployment-related PTEs); 4) post-deployment stress and trauma (exposure to PTEs following deployment, exposure to everyday/chronic stressors); 5) psychopathology (PTSD, depression, alcohol and substance use, abuse and dependence); 6) coping methods (acceptance, self-compassion, emotion regulation, attribution style, mindfulness, psychological flexibility, active coping); 7) multi-dimensional functioning; 8) response style/validity; and 9) information from VA electronic health records such as diagnoses, progress notes, medications, lab or radiology findings, etc.

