over time (Figure H1a). The statistical power of the target effect, the direct arrow from the treatment targets to the slope of functional impairment over time, is evaluated. Given the proposed sample size (500 participants with 4 repeated measures), the power for detecting a medium direct effect (based on our preliminary analyses) from the treatment targets to the slope of functional impairment is  $> .90$ . GMM will be used to test Hypothesis 1b (Figure H1b). Based on our preliminary studies, the statistical power for detecting a three-class solution is larger than .90 given the proposed sample size (500 participants). We calculated statistical power for the effects of the novel and established treatment targets on latent class membership. Assuming a small to medium effect size (odds-ratio = 1.82, which roughly corresponds to Cohen's  $d$  of 0.34), the power of the treatment targets on predicting class membership ranged from .72 to .91. In Hypothesis 1c, risk for SDV is measured in multiple ways including a continuous variable (severity of suicidal thoughts), a frequency/count variable (number of instances of NSSI), and a dichotomous variable (attempted suicide). A latent factor will be created and analyzed in Mplus which uses the MLR estimation to handle non-normally distributed variables. The longitudinal property of this latent factor will be examined via the longitudinal measurement invariance. Once the risk for SDV factor model is confirmed, we will regress it on the latent class membership (based on H1b results), hypothesizing that the most severely impaired class will predict greater risk of SDV. The proposed mediation model in Hypothesis 1d (i.e., the treatment targets mediate the effects of mental and physical wounds on functional impairment and risk for SDV over time) will be tested by using Mplus MODEL INDIRECT with bootstrap confidence intervals. By assuming a medium mediation effect, the corresponding statistical power is larger than .80 with our proposed sample size. We used conditions and parameters that are broadly based on our own data, prior clinical studies, and published Monte Carlo studies. Effect sizes estimates were in the small-to-medium range. The number of repeated measures is based on the current design. In brief, we are confident that the parameters and conditions are very close to our proposed study conditions.

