The DSMP will consist of examination of the accruing study data for indications that participating Veterans are being appropriately referred for treatment when necessary. The PI and doctoral-level staff will provide ongoing supervision through weekly Diagnostic Review Groups (DRG), which will include discussion of referral information for each Veteran who is identified as having mental health difficulties. In addition, self-report data will be reviewed by the PI or her staff. Specifically, each time a participant completes the PHQ-9, item 9 (suicidality) will be visually scanned to make sure that participants are not endorsing suicidal intent. Any participants who are identified as at risk for suicidality (i.e., endorse "Several days" or "More than half the days" or "nearly every day" on PHQ-9 item #9 asking how often in the last two weeks the Veteran was thinking s/he would be better or dead or was wanting to hurt him/herself in some way) will be contacted by the PI or a trained clinician to conduct a clinical risk assessment, safety plan (if necessary), and appropriate clinical referral. Additionally, each time the participant completes the Treatment Involvement Form (TIF), it will be reviewed for serious adverse events occurring during the study period by the PI or trained study staff. The PI has the responsibility of reporting adverse events to the IRB, in accordance with federal regulations. If a participant is hospitalized in response to a crisis, determination as to continuation in the study will be handled on a case-by-case basis. Veterans who feel that participation in the study is overwhelming can certainly discontinue. Veterans will also be given the option of skipping an assessment point versus discontinuing. In many cases, it may be beneficial for the Veteran to continue, for example: 1) Although not a substitute for good clinical care, Project SERVE: FX can serve as an "extra set of eyes" to monitor how Veterans are doing over time; and 2) study discontinuation may feel penalizing for Veterans who have reported suicidality, when such reporting should be encouraged. Additionally, understanding suicidality over time is a crucial area of scientific research that has benefit for our understanding of the adjustment process following deployments, and for developing prevention programs for both Veterans and society at large.

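### H1d: the only Phase III depression scale contains an item on suicidal and self-harm thoughts, so the depression-to-SDV path should use PHQ-9 items 1-8 and adjust for baseline SDV

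*Combined protocol and SAP*

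**What the plan says.** **Depression measure.** Table 1 (Phase III Assessment Instruments) describes the PHQ-9 as a "Self-report measure used for screening, diagnosing, and monitoring depression", given at all four waves, and adds that "Question 9 screens for suicidal ideation". The Data and Safety Monitoring Plan describes the item as asking how often the Veteran was "thinking s/he would be better or dead or was wanting to hurt him/herself in some way".

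**No second depression instrument.** The Phase III diagnostic interview is limited: "Modules administered from this widely used screening Interview to assess for exclusionary criteria (manic/hypomanic episode and psychosis". The SCID, which covered depression, appears only in the Phase I and Phase II tables. Assessment Procedures also lists "information from VA electronic health records such as diagnoses, progress notes, medications, lab or radiology findings, etc", but no Aim 1 model is said to use record diagnoses.

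**Outcome.** The Analytical Plan measures SDV risk through "a continuous variable (severity of suicidal thoughts), a frequency/count variable (number of instances of NSSI), and a dichotomous variable (attempted suicide", combined in a latent factor.

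**Model.** H1d states that "the treatment targets mediate the effects of mental and physical wounds on functional impairment and risk for SDV over time". Specific Aim 1 names depression as one of five conditions, with PTSD, chronic pain, TBI and AUD.

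**Role codes.** The key to Table 1 reads "DV = Dependent/Outcome Variable; PV = Predictor Variable; Med = Mediator; CV = Covariate". The PHQ-9 is coded as both mediator and outcome, not as predictor or covariate.

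**What is not said.** The plan does not name the depression score for any SDV model, and it mentions neither an eight-item score nor an analysis without item 9. Adjustment for prior level is stated for functional impairment but not for SDV. The Phase III covariates are not listed.

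**The concern.** H1d asks how much of the link from depression to later SDV runs through the treatment targets. If the depression score already holds an item on suicidal and self-harm thoughts, part of that link is one measure of ideation predicting another. Taking the depression score at an earlier wave does not cure this, because ideation tends to persist. Without a baseline SDV term, item 9 would act as an unlabelled baseline measure of the outcome inside the depression score. The total and direct effects of depression would then shift, and with them the share credited to the targets, which is what H1d is meant to estimate.

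**Working it through.** **1. Where the overlap can arise.**

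| Model | Predictor side | Depression score present? |
|---|---|---|
| H1c | Latent class from the H1b growth mixture model of functioning; the plan's functional composite uses WHODAS 2.0, IPF, QLS and Values Tracker | No |
| H1 regressions on SDV | Treatment targets plus unlisted covariates | Only if depression is one of the covariates |
| H1d, SDV part | Mental and physical wounds, then treatment targets | Yes, depression is one of the wounds |

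The role codes fit this reading. The PCL-5, AUDIT, TBI interview and Chronic Pain Screen, which measure the other Aim 1 conditions, all carry the mediator code, as the PHQ-9 does. The treatment-target scales (AAQ-II, SCS-SF, DERS-Brief, FFMQ, INQ, MIES) carry the predictor code. The PHQ-9 therefore sits with the wounds. Of these condition measures it alone also carries the outcome code.

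**2. The plan's nearest figure.** No number in the plan addresses the overlap. The closest is power above .80 for a medium mediation effect in H1d at N = 500. Alpha and the path values are not given, so the figure cannot be reproduced exactly. Assuming two-sided alpha .05 and joint significance of standardised paths a and b:

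power = Φ(a/√[(1−a²)/n] − 1.96) × Φ(b/√[(1−b²)/(n(1−a²))] − 1.96)

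- a = b = .26: .9999 at n = 500 and .999 at n = 400 (20% lost).
- a = b = .14: .78 at n = 500 and .65 at n = 400.

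The stated figure is plausible for medium paths, and the overlap does not contradict it.

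**3. Size of the overlap (illustration).** The documents give none of these inputs, so all are assumptions: s8 and s9 are the SDs of the eight-item sum and of item 9, r89 is their correlation, and r8 and r9 are their correlations with later SDV.

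r(total, SDV) = (s8·r8 + s9·r9) / √(s8² + s9² + 2·r89·s8·s9)

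Central case: s8 = 5.5, r89 = .5.

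- Low: s9 = .6, r9 = .45. Denominator √(30.25 + .36 + 3.30) = 5.823.
- High: s9 = .8, r9 = .50. Denominator √(30.25 + .64 + 4.40) = 5.941.

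| r8 | Low | High | Rise |
|---|---|---|---|
| .25 | (1.375 + .27)/5.823 = .282 | (1.375 + .40)/5.941 = .299 | .03 to .05 (13-20%) |
| .40 | (2.20 + .27)/5.823 = .424 | (2.20 + .40)/5.941 = .438 | .02 to .04 (6-9%) |

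Wider grid: s8 5 to 6, s9 .4 to .8, r89 .4 to .6, r8 .2 to .4, r9 .5 to .7.

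- Smallest rise: (6×.4 + .4×.5)/√(36 + .16 + 2.88) = 2.60/6.248 = .416, a rise of .016.
- Largest rise: (5×.2 + .8×.7)/√(25 + .64 + 3.2) = 1.56/5.370 = .290, a rise of .090.

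**4. Are the inputs coherent?** Given item 9, the standardised coefficient for the other eight items is (r8 − r9·r89)/(1 − r89²).

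- Central case, r8 = .25: (.25 − .225)/.75 = .03, and (.25 − .25)/.75 = 0.
- Central case, r8 = .40: .175/.75 = .23, and .15/.75 = .20.
- Central case, r8 = .10: −.125/.75 = −.17, and −.15/.75 = −.20. The other eight depression items would then appear protective, so this case is set aside.
- Grid maximum: (.2 − .28)/.84 = −.10, also slightly negative. The largest rise on the grid without a negative coefficient is at r8 = .3 with the same other inputs: (1.50 + .56)/5.370 = .384, a rise of .084.

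**5. Not all of the rise is overlap.** If item 9 were related to SDV no more strongly than the other eight items together (r9 = r8 = .25), the total would still give (1.375 + .15)/5.823 = .262 or (1.375 + .20)/5.941 = .265. In the .25 example, about .01 to .02 of the .03 to .05 would therefore arise without special overlap.

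**The case against.** The strongest reply is that the plan never says the PHQ-9 total predicts SDV. The scale is coded as mediator and outcome, record diagnoses are collected, and H1d could use a category instead of a score. This stands in part: use of the total is an inference. But the PHQ-9 is the only depression instrument listed, it shares its code with the other condition measures, and no other depression source is assigned to Aim 1.

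A second reply is that item 9 belongs to the depression construct, since Table 1 says the scale follows diagnostic criteria, so neither score is the true one. That is fair, and it is a reason to report both scores. When SDV is the outcome, though, the score free of outcome content is the better primary choice.

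A third reply is that dropping item 9 does not stop ideation carrying over between waves, because the other eight items are themselves correlated with ideation. This stands in full, and it is why baseline SDV adjustment has to accompany the rescoring.

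A fourth reply is that the shift is small. At r = .25 it is .03 to .05, against a standard error of (1 − .0625)/√499 = .042 at N = 500 or .047 at N = 400. The exclusion of Veterans whose current suicidal or homicidal risk warrants crisis intervention may also narrow item 9's spread and favour the lower values. This stands, though a systematic shift does not shrink as the sample grows.

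Readers might also infer more than the documents support:

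- **That every SDV model is affected.** H1c has no depression predictor, and the Phase III covariates are not listed. The only itemised covariate list, in Phase II, does not include depression.
- **That an outcome item sits inside the predictor.** Dedicated SDV instruments exist (Columbia, CANDI, BSSI), and nothing makes item 9 an SDV indicator. The overlap is in content.
- **That the inflation reaches 41-60%.** The arithmetic for .10 becoming .14-.16 is correct, but it needs the negative coefficient shown above.

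**Conclusion.** The point holds for the SDV part of H1d, and conditionally for any H1 SDV regression that includes depression as a covariate. The only listed depression scale shares content with the SDV factor, and no planned step deals with it. If the total score is used, the depression-SDV correlation is raised by roughly .02 to .09 on assumed inputs, with the upper end needing item 9 to correlate .7 with later SDV. The direction rests on item 9 being related to SDV strongly enough. In the central case r9 need only exceed about .54 to .55 of r8, from (5.823 − 5.5)/.6 and (5.941 − 5.5)/.8. These are zero-order correlations; the change in the indirect effect or in the share mediated was not computed. Nothing here shows a stated sample size or power to be wrong. The point is a free improvement, not a flaw that threatens the study.

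**What to change.** 1. In the H1d SDV model, and in any H1 SDV regression with depression as a covariate, score depression from PHQ-9 items 1-8. Report the full PHQ-9 as a sensitivity analysis.
2. Adjust those models for baseline SDV, using the Columbia, CANDI and BSSI data already collected at baseline. This deals with carry-over directly and matches the aim of prospective prediction.
3. Name the depression score used in each SDV model and list the Phase III covariates.
4. Item 9 may serve as an auxiliary variable for missing SDV data. It is collected at all four waves, whereas the Columbia, CANDI and BSSI are collected only at baseline and 24 months, and the plan allows for up to 20% missing data.

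Leave H1c, the functioning models and the safety review of item 9 as they are. The cost is one scoring line, one extra model run and a few sentences in the Analytical Plan, with no new data collection.
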